#### 9. EFFICACY ASSESSMENT

The primary efficacy endpoint of Part 1 of this study is 1-year survival, i.e., the proportion of patients who are alive at 1-year measured from the date of the randomization. Secondary efficacy endpoints are the rate of CR, CRp, PR or CRi or hematological improvement and their corresponding durations, transfusion requirements and number of hospitalized days. The primary efficacy endpoints of Part 2 of this study are the rate of clinical benefit response (CR, CRp, PR, or major HI) and the rate of complete response (CR or CRp). Secondary efficacy endpoints are response durations, transfusion requirements, number of hospitalized days, and overall survival. The primary efficacy endpoint of Part 3 and 4 of this study is 1-year survival rate. Secondary efficacy endpoints are the rate of clinical benefit response (CR, CRp, PR, major HI or SD) and their corresponding durations, transfusion requirements, number of hospitalized days and overall survival.

The tissue samples supporting the diagnosis of AML or MDS, and the responses to sapacitabine may be submitted for central review.

Table 6 Response Criteria

Passansa Description					
Response	Description				
Complete Remission (CR) 	Normalization of peripheral neutrophils to ≥1000 /µL, platelet to ≥100,000/µL within 2 weeks of bone marrow biopsy/aspirate, and bone marrow to ≤5 % blasts; independent of transfusions*; and no extramedullary leukemia.				
Complete remission with incomplete platelet count recovery (CRp) 	Normalization of bone marrow to $\leq$ 5% blasts; peripheral neutrophils $\geq$ 1000 /µl, platelet $<$ 100,000 /µL within 2 weeks of bone marrow biopsy/aspirate; independent of transfusions*; and no extramedullary leukemia.				
Complete remission with incomplete blood count recovery (CRi) 8	Normalization of bone marrow to $\leq$ 5% blasts; peripheral neutrophils $<1000~/\mu$ L, platelet $<100,000/\mu$ L within 2 weeks of bone marrow biopsy/aspirate; independent of transfusions *; and no extramedullary leukemia.				
Partial Remission (PR) 8	Normalization of peripheral neutrophils to $\geq 1000 \ / \mu L$ , platelet to $\geq 100,000/\mu L$ within 2 weeks of bone marrow biopsy/aspirate, $\geq 50\%$ decrease in bone marrow blasts over pretreatment but still >5%; independent of transfusions * .				
Hematological improvement (HI) 9	Major response:				

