	(1) For patients with pretreatment hemoglobin < 11 g/dL, >2g/dL increase in hemoglobin; for RBC transfusion - dependent patients, transfusion - independence*				
	(2) For patients with a pretreatment platelet count <100,000/mm³, an absolute increase of ≥30,000/mm³; for platelet transfusion-dependent patients, stabilization of platelet counts and platelet transfusion independence*.				
	(3) For patients with absolute neutrophil count (ANC) $< 1,500/$ mm  before therapy, $\ge 100\%$ increase, or an absolute increase $> 500/$ mm  , whichever is greater.				
	Minor response:				
	(1) For patients with pretreatment hemoglobin < 11 g/dL, 1-2 g/dl increase in hemoglobin; for RBC transfusion – dependent patients, 50% decrease in transfusion requirements.				
	(2) Platelet response: for patients with a pretreatment platelet count $<100,000/\text{mm}^3, \ge 50\%$ increase in platelet count with a net increase $>10,000/\text{mm}^3$ but $<30,000/\text{mm}^3$ .				
	(3) For patients with absolute neutrophil count (ANC) $< 1,500/$ mm  before therapy, $\ge 100\%$ increase, but absolute increase $< 500/$ mm  .				
Stable disease (SD)**	Failure to achieve at least HI, but no evidence of clinically significant progression for > 16 weeks.				

\*independent of transfusions or transfusion –dependence refer to no packed red blood cell transfusion for 2 weeks and no platelet transfusion for 1 week .

Transfusion requirements for each patient are defined as the number of weeks during which at least one transfusion for red blood cells (RBCs) or platelets is administered and the mean number of units of RBC and platelet transfusions administered per month.

CYCLACEL LTD CONFIDENTIAL 34 of 56

\*\* for Part 2, 3 and 4 of the study only

Clinical benefit is defined as the achievement of CR, CRp, PR, major HI or SD. The duration of clinical benefit is measured from the earliest time when the patient achieved CR, CRp, PR or major HI to the first date when the major HI is lost; if the patient only achieved SD, the duration of clinical benefit is measured from the date of randomization or registration to the first date when clinically significant progression of disease is observed.

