#### 11.2. Sample Size for Part 2 of the Study

The Part 2 of the study is an open-label, single arm phase II study in elderly patients with previously untreated AML and significant concomitant medical illnesses as measured by having HCTCI of 2 and higher. There are two co-primary efficacy endpoints, the rate of clinical benefit response (CR, CRp, PR, major HI or SD) and the rate of complete response (CR or CRp). Secondary endpoints are response duration, transfusion requirements, number of hospitalized days, overall survival, and safety. Statistically, the purpose of the trial is to reject sapacitabine from further study in elderly AML patients with HCTCI of 2 and higher if it were insufficiently active, and to accept it as active if it were truly active.

The trial is based on the following assumptions:

- The inactivity cut-off is chosen equal to 5% clinical benefit response; the activity cut-off is equal to 30% clinical response rate; hence, the hypotheses of interest are  $H_0$ :  $r \le 5\%$  against  $H_A$ :  $r \ge 30\%$ , where r is the response rate.
- The type I error rate ( $\alpha$ , probability of accepting an insufficiently active treatment, a false positive outcome) is set to 5%.
- The type II error rate ( $\beta$ , probability of rejecting an active treatment, a false negative outcome) is set to 5%.

Under these assumptions, a two-stage design uses the following decision rule:

After treating up to 12 evaluable patients defined as those who have completed at least one treatment cycle,

- If no response is observed, declare the treatment insufficiently active and no more patient will be treated with this dose regimen
- If at least one response is observed, add patients to reach a maximum of 24 patients and
  - o If three responses or less are observed, declare the treatment insufficiently active
  - o If at least four responses are observed (an observed response rate of at least 17%), declare the treatment sufficiently active and add patients to reach a maximum of 36 patients.

The dose regimen will be considered active if the clinical benefit rate is at least 30% or the

rate of CR/CRp is at least 20%. Since the trial has two co-primary endpoints, the 97.5% confidence interval is calculated for each of the two endpoints. Assuming that the true response rate is equal to 30% clinical benefit rate and 20% CR/CRp, 36 patients are required for the lower bound the of the 97.5% confidence interval to exclude 5% for both endpoints.

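### Table 6 lets a count taken after a transfusion qualify as major hematological improvement in patients not classed as transfusion-dependent, and it does not clearly define that class

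*Combined protocol and SAP*

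**What the plan says.** Table 6 in Section 9 gives the response criteria. CR must show "bone marrow to ≤5 % blasts; independent of transfusions*; and no extramedullary leukemia", and CRp, CRi and PR carry the same starred condition. The footnote explains the star as "no packed red blood cell transfusion for 2 weeks and no platelet transfusion for 1 week".

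Major HI is split by transfusion status:

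- Red cells: "For patients with pretreatment hemoglobin < 11 g/dL, >2g/dL increase in hemoglobin"; then, separately, "for RBC transfusion - dependent patients, transfusion - independence".
- Platelets: "For patients with a pretreatment platelet count <100,000/mm³, an absolute increase of ≥30,000/mm³"; then, separately, "for platelet transfusion-dependent patients, stabilization of platelet counts and platelet transfusion independence".

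Only the second half of each clause carries the star.

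Major HI counts as clinical benefit. Section 11.2 gives Part 2 "two co-primary efficacy endpoints, the rate of clinical benefit response (CR, CRp, PR, major HI or SD") together with the CR/CRp rate, and sets the null as follows: "The inactivity cut-off is chosen equal to 5% clinical benefit response". Section 11.3.1 uses clinical benefit for futility and expansion in Parts 3 and 4, where the primary endpoint is 1-year survival. Section 11.1.1 counts major HI toward expansion of an MDS dosing schedule in Part 1.

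**The concern.** Section 6.5 allows blood products as supportive care, and Section 1.6 lists myelosuppression as an expected major toxicity. Table 5 schedules blood counts on Days 8 and 15 of Cycle 1 and on Day 1 of later cycles, with nothing to separate them from a transfusion. A patient outside the transfusion-dependent class who is transfused on study, and whose next count stands far enough above the pretreatment value, meets the written criterion. A supportive measure would then be scored as drug benefit.

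No other provision catches this. Sections 6.5, 9, 11.2 and 11.4 contain no rule that sets aside counts taken after a transfusion. The second assessment in Section 9 confirms recurrence or progression, not response. Section 3.7 lets the investigator's case report form serve as source data for response, and central review in Section 9 is optional. The written definition is therefore the main safeguard for an endpoint judged against a null of only 5%.

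**Working it through.** **1. The text side by side**

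| Table 6 category | Transfusion-free condition |
|---|---|
| CR, CRp, CRi, PR | yes, all patients |
| Major HI, red cells and platelets, transfusion-dependent | yes |
| Major HI, red cells, other patients | none |
| Major HI, platelets, other patients | none |

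Table 6 does not say who is transfusion-dependent or when this is judged. Its footnote attaches one meaning, a period without transfusion, to both independence and dependence. That wording describes independence. The once-a-month definition in Section 8.1 serves adverse event grading.

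**2. Part 2 gate (Section 11.2): at least 1 response in 12, then at least 4 in 24**

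P(pass) = P(X24 ≥ 4) − P(X12 = 0) × P(Y12 ≥ 4), where X24 and X12 are responses among the first 24 and 12 patients and Y12 those among the second 12. All are binomial with rate p.

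The plan's own figures come first. It sets both error rates at 5%.

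- p = 5%: 0.0298 − 0.0012 = 0.0286, within the 5% limit.
- p = 30%: 0.9576 − 0.0070 = 0.9506, matching 95% power.

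The same formula at inflated rates (assumption: misclassification adds 5 or 10 points to a true 5%):

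- p = 10%: 0.2143 − 0.0072 = 0.207.
- p = 15%: 0.4951 − 0.0131 = 0.482.

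**3. Part 2 final criterion (Section 11.2): clinical benefit of at least 30% in 36 patients**

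0.30 × 36 = 10.8, so 11 responses are needed. The chance of passing both looks and then reaching 11 of 36, by summing exact binomial terms over all three groups of 12, is about 0.0006 at p = 10% and 0.014 at p = 15%.

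**4. Futility in Parts 3 and 4 (Section 11.3.1): stop at 0 of 10 or at most 1 of 17**

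P(stop) = (1−p)^10 + 10p(1−p)^9 × (1−p)^7.

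| Rate counted as benefit | Computed | Table 9 |
|---|---|---|
| 5% | 0.599 + 0.220 = 0.819 | 0.822 |
| 10% | 0.349 + 0.185 = 0.534 | 0.54 |
| 15% | 0.197 + 0.111 = 0.308 | 0.313 |

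**5. Another way to state the assumption**

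Let f be the share of true non-responders scored as major HI only because of a transfusion. The counted rate is 0.05 + 0.95f: 9.75% at f = 5% and 14.5% at f = 10%. P(pass 4/24) is then 0.195 and 0.454, and P(stop) 0.547 and 0.327. The picture is the same.

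**The case against.** **The footnote may already protect.** It mentions dependence as well as independence, and the transfusion-dependent clauses give no time point. One could read a patient transfused within the window as dependent and so required to show independence. But the footnote's words describe a period without transfusion, so they cannot define dependence as written. The ambiguity is part of the defect.

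**Four of 24 is not the end of Part 2.** This stands. Section 11.2 calls that result sufficiently active, but then enrolls to 36 and considers the regimen active at 30% clinical benefit or 20% CR/CRp. A reader might infer from 0.21-0.48 that an inactive regimen would often meet the final criterion. The documents do not support that: by the clinical benefit route the chance stays near 0.001-0.014, and CR and CRp already require freedom from transfusion. The likely cost is up to 12 further patients.

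**Stable disease absorbs part of the effect.** This also stands. A patient wrongly scored as HI who goes more than 16 weeks without clinically significant progression counts as clinical benefit anyway. Only those who would fail that test inflate the rate. (Section 9's statement of the Part 2 endpoint omits stable disease; Section 11.2 and the clinical benefit definition include it.)

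**The 5-10 points have no source in the documents.** True. The rise is measured from the pretreatment value, and myelosuppression lowers counts as well as prompting transfusion. It is tempting to infer that the drug's toxicity must generate responses; the documents show only that the rule permits it.

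**The HI row cites published criteria.** Whether these carry a transfusion rule cannot be checked here, and Table 6 states none for these clauses.

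**Conclusion.** The gap is real and rests on the text alone. For patients not classed as transfusion-dependent, the major HI hemoglobin and platelet clauses lack the condition that every remission category carries, and the class itself is not clearly defined.

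The effect on decisions is conditional. If misclassification raised a true 5% rate to 10-15%, an inactive regimen would be several times more likely to pass the Part 2 gate, and a futile arm in Part 3 or 4 noticeably less likely to stop. The final Part 2 clinical benefit criterion would remain hard to reach. These figures are upper readings of that assumption, because they make no allowance for stable disease.

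A reader might also infer that primary endpoints throughout the trial are affected. Only Part 2 has clinical benefit as a primary endpoint. In Parts 3 and 4 it is secondary but governs futility and expansion; in Part 1 major HI bears on MDS expansion. One-year survival as an endpoint, the neutrophil clause and the CR/CRp endpoint are untouched.

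**What to change.** Three wording changes to Table 6:

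1. Add to the major HI hemoglobin clause that the qualifying value must follow at least 2 weeks without red cell transfusion, and to the platelet clause that the qualifying count must follow at least 1 week without platelet transfusion. These are the footnote's existing windows. A star alone would not do, because the footnote explains a phrase that these clauses do not contain.
2. Correct the footnote so that it refers to transfusion-independence.
3. State that transfusion dependence is judged at baseline, and define it. Table 5 already records transfusions over the 8 weeks before the first dose.

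Transfusions are already recorded on study, and the windows are already needed to score CR and PR, so no visit, sample size or treatment rule changes. Responses already recorded would need re-scoring under the new wording. The observed clinical benefit rate may be slightly lower.

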- 4.1.8. Patients must be at least 2 weeks from prior systemic therapy for AML or MDS, radiation therapy, major surgery, or other investigational therapy, and have recovered from clinically significant toxicities of these prior treatments. Patients with ≥ 50,000 WBC in peripheral blood may receive hydroxyurea to control the WBC <50,000 prior to starting sapacitabine if this is considered by the treating physician to be in the best interest of the patient.
- 4.1.9. All men of reproductive potential must agree to practice effective contraception for 4 weeks prior to study entry, during the entire study period and for one month after the study unless documentation of infertility exists.
- 4.1.10. Ability to understand and willingness to sign the informed consent form

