### 4.3. Removal of Patients from Therapy

Patients have the right to withdraw from the study at any time for any reason. The investigator has the right to withdraw patients from the study according to his/her discretion. When a patient discontinues treatment early, every effort will be made to conduct a post-treatment follow-up visit within 4 weeks after the last dose of study drug or prior to the initiation of new treatment. This post-treatment evaluation may be conducted over the phone if the patient is unable to return to the clinic. The reason(s) for withdrawal must be recorded.

Criteria for terminating participation in the study are listed below:

- Clinically significant progressive disease defined as > 50% increase in the percentage of blasts in bone marrow or peripheral blood over baseline to reach at least 20% blasts in bone marrow or peripheral blood by two assessments while on treatment with an adequate dose
- Lack of efficacy refers to treating physician's judgment that patients are unlikely to benefit from continuation of treatment despite not meeting the criterion of clinically significant progressive disease.
- Unacceptable toxicity
- Patient withdrawal of consent for treatment
- Investigator's discretion that it is in the best interest of the patient to withdraw
- Intercurrent illness: a condition, injury, or disease unrelated to cancer in the opinion of the investigator, that renders continuing sapacitabine treatment unsafe or regular follow-up impossible

- General or specific changes in the patient's condition that renders the patient ineligible for further treatment
- Noncompliance with study medication or protocol-required evaluations and followup visits
- Termination of the clinical trial by the sponsor

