The duration of CR, CRp, PR or CRi or hematological improvement is measured from the time when response criteria are first met until the first date that recurrent or progressive disease is documented. To avoid premature discontinuation of patients who have had a temporary flare of the disease due to treatment interruptions, dose reductions, acute infection or other plausible explanations, a second assessment should be performed in these patients to confirm the recurrence or progression of disease.

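### A count-based major hematological improvement needs only one unconfirmed blood count, so ordinary fluctuation can score as response

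*Combined protocol and SAP*

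**What the plan says.** Table 6 (Section 9) defines three count-based routes to major HI, each as a change from the pretreatment value:

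- Platelets: "For patients with a pretreatment platelet count <100,000/mm³, an absolute increase of ≥30,000/mm³".
- Hemoglobin: "For patients with pretreatment hemoglobin < 11 g/dL, >2g/dL increase in hemoglobin".
- Neutrophils, if below 1,500 before therapy: a doubling or a rise of more than 500, whichever is larger.

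None of these asks for a second count, a minimum duration or an averaged baseline. Section 9 dates a response from the first time its criteria are satisfied. Footnote g of Table 5 allows the Cycle 1 Day 1 blood count to be omitted when the pre-study one is recent, so the baseline can be one value.

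Other criteria in the protocol do carry a time element or a repeat:

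- Transfusion independence means "no packed red blood cell transfusion for 2 weeks and no platelet transfusion for 1 week".
- Stable disease (SD) is "Failure to achieve at least HI, but no evidence of clinically significant progression for > 16 weeks".
- Progression under Section 4.3 must be shown "by two assessments while on treatment with an adequate dose".
- After a suspected temporary flare, Section 9 says "a second assessment should be performed in these patients to confirm the recurrence or progression of disease".

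Major HI is sufficient by itself for the composite: "Clinical benefit is defined as the achievement of CR, CRp, PR, major HI or SD". That composite is a Part 2 co-primary endpoint and drives the 4-of-24 rule (Section 11.2). It also drives the Parts 3 and 4 futility and expansion rules (Section 11.3.1). Major HI enters the Part 1 MDS expansion trigger directly (Section 11.1.1).

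**The concern.** Blood counts vary from visit to visit without any change in disease. When one low baseline value and one high later value are enough, some patients with no real improvement will qualify, and each further count gives another chance. The study is open label, Section 3.7 allows the investigator's response entry to serve as source data, and central review in Section 9 is optional. No later step is therefore certain to remove a one-count response.

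In Parts 1, 3 and 4 there is a second route. Section 4.1.8 sets this washout: "Patients must be at least 2 weeks from prior systemic therapy for AML or MDS". A baseline drawn soon after prior therapy may still be recovering. The same item requires recovery from clinically significant toxicities, which softens the point, but it does not require stable counts.

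At stake are the error rate of the Part 2 rule at 24 patients, the ability of the Parts 3 and 4 futility rule to stop an inactive arm, the Part 1 MDS expansion trigger, and the reported HI rates.

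**Working it through.** **1. Reproduce the plan's figures.**

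Part 2 (Section 11.2): stop at 0 of 12; sufficiently active at 4 or more of 24; null 5%, alternative 30%, both error rates 5%.

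P(pass) = Σ over x₁ ≥ 1 of P(X₁ = x₁; n = 12) × P(X₂ ≥ 4 − x₁; n = 12).

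At 5%: 0.3413 × 0.0196 + 0.0988 × 0.1184 + 0.0173 × 0.4596 + 0.0022 = 0.0286. At 30% the result is 0.951. Both agree with the stated limits.

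Parts 3 and 4 (Table 9): stop at 0/10 or 1/17.

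P(stop) = P(0/10) + P(1/10) × P(0/7).

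At 5%: 0.5987 + 0.3151 × 0.6983 = 0.819, against 0.822 in Table 9. The other rows agree within 0.006.

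**2. How often could one count mislead?**

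The documents give no within-patient variability, so this step is an assumption. Take a baseline B and on-study counts Y₁ and Y₂, independent and log-normal with the same mean m and coefficient of variation c, where σ² = ln(1 + c²). There is no true change. False platelet HI occurs if either Y exceeds B by at least 30,000. Two on-study counts represent a patient who leaves early. Simulated rates:

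| True platelet level | CV 15% | CV 20% | CV 25% |
|---|---|---|---|
| 20,000 | 0% | 0% | <0.1% |
| 30,000 | 0% | 0.1% | 0.8% |
| 60,000 | 2% | 7% | 14% |
| 80,000 | 7% | 16% | 23% |

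Requiring both counts to qualify reduces the 60,000 row to about 0.1%, 0.4% and 1.2%.

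For a patient who stays on study, which is the relevant case for the Part 1 MDS trigger, four cycle Day 1 counts around 60,000 give 4%, 13% and 24%. Requiring two consecutive qualifying counts reduces these to 0.1–3.1%.

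**3. Carry it to the decision rules.**

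Let f be the share of patients without other benefit who are falsely scored as major HI. The observed rate is then p + (1 − p)f. With p = 5%:

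| f | Observed rate | Part 2: P(≥4/24) | Parts 3/4: P(stop) |
|---|---|---|---|
| 0 | 5.0% | 2.9% | 82% |
| 1% | 5.95% | 4.9% | 76% |
| 2% | 6.9% | 7.7% | 71% |
| 5% | 9.75% | 19.5% | 55% |

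For example, at f = 5% the Parts 3/4 figure is 0.3585 + 0.3873 × 0.4877 = 0.547. Slightly more than 1% false HI takes the 24-patient rule past its stated 5%.

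**4. The later Part 2 criterion.**

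At 36 patients, 30% benefit means at least 11 (0.30 × 36 = 10.8). At f = 10% the observed rate is 0.05 + 0.95 × 0.10 = 14.5%, and P(≥11/36) = 1.1%. At f = 20% the observed rate is 24% and the probability is 22.9%.

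**The case against.** The strongest reply is that most patients with flat counts are not at issue. In Parts 2 to 4 a patient without progression for more than 16 weeks is SD and already counts as clinical benefit, so a false HI changes nothing for that patient. One sentence in Section 9 omits SD from the Part 2 composite, but the objectives, the definition under Table 6 and Sections 11.2 and 11.4 all include it. This objection stands for Parts 2 to 4. The patients who matter there leave or progress early, have fewer counts and often have falling ones. It does not help the Part 1 MDS trigger, which leaves SD out.

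Several stronger readings are tempting, and the documents do not support them:

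- **A large false-positive rate for Part 2 as a whole.** With 10% false HI the 4-of-24 step passes 45% of the time at a true 5%. But accrual then continues to 36, where the benefit criterion is met only about 1% of the time. The CR/CRp route does not use HI.
- **Every scheduled count is a fair chance to qualify.** Day 8 and Day 15 fall during or just after dosing with a myelosuppressive drug, so a flat mean is not credible there.
- **Recovery from prior therapy inflates Part 2.** Section 4.2 excludes prior systemic AML therapy, and hypomethylating or cytotoxic therapy for preceding MDS or MPD, from Part 2. Fluctuation is the route there.
- **The protocol confirms bad news but never good news, so noise runs only towards benefit.** The second assessment in Section 9 is there to avoid premature discontinuation after a flare. Loss of major HI is also unconfirmed, so a one-count HI would appear as a short duration. A chance-high baseline can hide a real improvement.
- **Schedule selection is distorted.** Selection in Parts 1, 3 and 4 uses one-year survival. Expansion is optional and also depends on 30-day deaths.

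It is also fair to say that the rate depends heavily on the assumed starting count and variability. At low platelet levels it is close to nil, and positive correlation between counts would lower it elsewhere.

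**Conclusion.** The gap is real and nothing elsewhere in the documents closes it: a single count can establish a count-based major HI. Its effect is limited. It adds to clinical benefit in Parts 2 to 4 only among patients who would not otherwise qualify, and it bears fully on the Part 1 MDS trigger and on reported HI rates.

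The rate of false HI cannot be read from the documents. It runs from near zero to about a quarter over the settings shown, assuming independent variation around a flat level. What does not depend on those settings is how little tolerance the 24-patient rule has. The Parts 3 and 4 futility rule also weakens materially at 5% false HI. The 36-patient benefit criterion withstands 10% false HI but not 20%. The Part 1 AML futility rule uses CR plus CRi and is untouched. This is a change the sponsor should make, but it does not invalidate the design.

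**What to change.** In Table 6, require the qualifying change in hemoglobin, platelets or neutrophils to be present at two consecutive scheduled cycle Day 1 counts, and date the response at the first of the two. Apply the same rule to the Part 1 HI rate and the Part 1 MDS expansion trigger.

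Do not add a fixed 4-week minimum. Visits may move by 3 days either way, so successive Day 1 counts on a 28-day cycle can be 28 − 6 = 22 days apart, and compliant patients would fail.

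The cost is a few words in Table 6, because a blood count is already scheduled on Day 1 of Cycle 2 and every later cycle. Observed HI rates will be slightly lower, and a patient who leaves after one qualifying count will not be scored as HI. Only response scoring changes.
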